- 4.1 Research setting: Participants will be recruited from clinics within Northwestern Medicine, or will be invited to come to our clinical research space on campus for three visits: Baseline, 3-month follow-up, and 6-month follow-up. Participants actively enrolled in the study during the COVID-19 pandemic will have extended time-frames to complete the 3-month follow-up and 6-month follow-up visit. Participants will come in for their 3-month follow-up visit when it is feasible and reasonably safe for them to do so and then will aim to complete their 6-month follow-up visit 3 months after their second visit. While participants are enrolled in the phone-based protocol, any outstanding in-person visits will be put on hold until the completion of the phone-based protocol.
- 4.2 Study design and rationale: The study is a two-group, three time-point experimental design. The two study groups are paper-and-pencil questionnaires versus a computerized talking touchscreen interface. The three time points are baseline, 3-month follow-up, and 6-month follow-up. The rationale for this design is that it will allow us to compare two models of administration as well as to examine how the psychometric properties of questionnaires change over time.

As a result of the COVID-19 pandemic, the study will add phone-based assessments to the study design. These study phone visits will be in addition to the original three time-points of the study design. The phone-based study visits will also happen at three time-points (baseline, 3-month follow-up, and 6-month follow-up). This design will allow us to examine the properties of the questionnaires that change over time as well as compare the phone-based assessments to the in-person assessments (via paper-and-pencil or talking touchscreen interface) that participants completed before the COVID-19 pandemic and, possibly, after the COVID-19 pandemic.

4.3 Description of research procedures and activities:

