assessment until the licensed psychologist/physician can arrive. Suicide prevention steps will be taken in the unlikely event that a participant has active suicidal intentions; these procedures include taking the participant to the Northwestern Medicine Emergency Department or notifying emergency services by calling 911.

During the phone-based protocol, the PHQ-9 questions will not be asked and no other questions that address suicidality are present in the phone-based protocol. During the informed consent process, the research coordinator will tell participants that if they appear to be a risk to themselves or others, the coordinator will call 911 to request emergency services. In the unlikely event that emergency services do need to be requested, the research coordinator will ask all participants their current location at the beginning of each call so that information is available for potential emergency service response. If the participant does not appear to be an imminent threat to themselves or others but would like mental health resources, we will email or mail (depending on participant preference) a copy of the mental health resource list to them.

4.5 Study Timeline. We anticipate recruitment of participants to begin March of 2018, preceded by a brief pilot-testing phase to ensure all procedures run smoothly. We aim to recruit 17 participants per month for three years to reach our local (i.e., Northwestern) target of *N* = 612. Each participant will be invited to complete a baseline (i.e., visit 1), three-month (i.e., visit 2), and six-month (i.e., visit 3) follow-up assessment. The first visit will take between 120-150 minutes and the second and third visits will last 60-90 minutes each. Recruitment for the phone-based protocol is anticipated to begin in July of 2020. Phone-based visits are expected to take approximately 60 minutes. We aim to enroll all 612 participants from the in-person protocol for the phone-based protocol. Each participant in the phone-based protocol will be asked to complete a baseline assessment (visit 1), three-month assessment (visit 2), and six-month assessment (visit 3). These 3 time-points are separate from their inperson visits. The final year of the project will be used for data analysis, manuscript writing, and study close-out.

4.6 Types of assessments completed.

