$$\text{item slope}_j = a_j + b1_j * \text{Health LiTT} + b2_j * \text{Administration Type} + b3_j * \text{Interaction}$$

where j is an index for the k items (8 items in this case).

We will use Mplus in conjunction with the aMNLFA²⁴ package of R. Following the MNLFA procedure outlined by Curran et al.,²⁵ we will test models allowing item parameters (intercept and slope) to vary as a function of hypothesized DIF variable, one item at a time, in order to arrive at a final model. We will use the final model to generate item characteristics curves (ICCs, which will show the estimated probabilities of endorsement for each item across different levels of meaning and purpose. Among non-invariant items, we will consider differences (due to DIF variables) in probability endorsement of 10% to be potentially meaningful scientifically. Using the final model, we will also plot meaning and purpose factor scores by healthy literacy and administration type to understand the relationship among these variables. For these analyses, we will use all available baseline data collected through March of 2020 ($N = 566$ English speakers).

Longitudinal analyses of Meaning and Purpose Predicting Quality of Life. In addition to examining DIF by health literacy in the NIH Toolbox Meaning and Purpose measure (as described above), cross-lagged panel analyses will be used to examine whether meaning and purpose predicts health-related quality of life (i.e., anxiety, depression, fatigue, pain intensity and interference, physical function, sleep disturbance, and disruption of social roles and activities) over time across the three study assessments. We will also identify covariates including sociodemographics associated with meaning and purpose (i.e., age, gender, financial strain, education, race/ethnicity, language). We hypothesize that greater meaning and purpose will prospectively predict greater quality of life at subsequent study assessments. We will only include participants who could have provided complete data before we ceased recruitment due to COVID-19. Thus, we will exclude participants who are 1) were enrolled on or after 16 September 2020, and 3) missing their 6-month assessment. In this way, data will not be systemically missing due to censoring from the COVID-19 pandemic (i.e., to be eligible, the person would have had sufficient time to complete all three assessments before the COVID-19 pandemic).

Exit Interview

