Hypothesis 1: Depression predicts pain at 6-month follow-up, mediated by sleep disturbance at 3-month follow-up: We hypothesize depression will be related to *more* sleep problems at 3-month follow up, which in turn will lead to *more* pain at 6-months. Depression at baseline will be operationalized by the PROMIS depression scale within the 57-item Profile. Note that we made an *a priori* decision to use PROMIS rather than the PHQ-9 for depression because the PHQ-9 contains questions about sleep whereas the PROMIS depression scale does not. We will assess sleep at 3-month follow-up using the PROMIS sleep disturbance subscale of the 57-item Profile. We will use two different PROMIS Profile scales to assess pain at 6-month follow-up: pain intensity and pain interference. These hypotheses were formulated before any data were examined.

To carry out these analyses, we will use the *mediate* package in R for these analyses. The form of the mediation is depression at baseline → worse sleep at 3mo → more pain at 6mo. We will first create the regression models for depression predicting sleep, and sleep predicting pain. Sleep as a mediator will be tested in the *mediate* package based on the 95% bca confidence intervals.

Hypothesis 2: Pain predicts depression at 6-month follow-up, mediated by sleep disturbance at 3-month follow-up: To examine bidirectional causality, we will analyze the mediation from Hypothesis 1 in the opposite direction, specifically Pain at baseline → worse sleep at 3mo → more depression at 6mo. The same mediation procedures will be used, as in Hypothesis 1, with two different pain measures as the initial covariate: pain intensity and pain interference.

Hypothesis 3: Sex will moderate mediation relationships found in Hypotheses 1 & 2. Given that depression disproportionately affects females when compared to males, we plan to conduct moderated

mediation for sex. We hypothesize sex will moderate the mediation, with female sex being associated with stronger associations among depression and sleep, and sleep and pain.

Exploratory analyses. We anticipate that age influences depression, sleep, pain, but have no directional hypothesis for age. Thus, age will be included as an exploratory variable in the above-mentioned mediations.

Statistical Analysis Plan Addendum: Vaccine Confidence Analysis from phone-based substudy (section added 10 March 2021)

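### The final sleep mediation takes Visits 2 and 3 at their nominal 3 and 6 months, although the protocol lets pandemic-delayed visits fall 10 months or more after baseline

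*Protocol*

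**What the plan says.** **Visit timing.** Protocol 4.1 provides that participants active during the pandemic "will have extended time-frames to complete the 3-month follow-up and 6-month follow-up visit". For Visit 2 the rule is open-ended: "Participants will come in for their 3-month follow-up visit when it is feasible and reasonably safe for them to do so". Visit 3 is tied to the actual Visit 2 and not to baseline: participants "then will aim to complete their 6-month follow-up visit 3 months after their second visit". For anyone in the phone study, "any outstanding in-person visits will be put on hold until the completion of the phone-based protocol". Protocol 4.2 gives the phone study its own baseline, 3-month and 6-month calls. Protocol 4.5 adds: "Recruitment for the phone-based protocol is anticipated to begin in July of 2020".

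**Sleep mediation.** Hypothesis 1 in the SAP section on sleep as a mediator is "Depression predicts pain at 6-month follow-up, mediated by sleep disturbance at 3-month follow-up". Hypothesis 2 reverses the direction over the same visits. The section plans an interim run for an October 2020 conference and a final run after the parent study has finished collecting data. It gives no visit window, no rule for late visits and no use of actual elapsed time.

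**Other longitudinal analyses.** The factor analysis under Study Timepoints (Table 3) uses Visits 1, 2 and 3 as labelled. The PCL-5 section, added in October 2024, uses all three time points and describes the interviews as spaced at three-month intervals. Only the longitudinal Meaning and Purpose analysis has a pandemic rule: "We will only include participants who could have provided complete data before we ceased recruitment due to COVID-19".

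**The concern.** A lagged path is an effect over a particular interval. The mediation is presented as baseline to 3 months to 6 months. If some visits labelled 3-month fall close to a year after baseline, the pooled coefficient mixes two different lags. The mixing affects different paths in different people. With Visit 2 outstanding at the pause, the baseline-to-sleep interval is stretched. With only Visit 3 outstanding, the sleep-to-outcome interval is stretched.

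Delayed visits also measure depression, sleep and pain during the pandemic, while baseline was measured before it. Part of an apparent lagged association could therefore be a calendar effect. At stake is whether the final result can be described as a 3-month or 6-month mediation at all.

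**Working it through.** The documents state no figure for elapsed time, so there is nothing to reproduce. The check is calendar arithmetic.

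**Inputs**
- Phone start: July 2020 (Protocol 4.5, an anticipated date). Mid-month, 16 July, is used first.
- Phone length: 6 months (Protocol 4.2).
- Pause of in-person visits: 16 March 2020. This is an assumption. The Meaning and Purpose DIF section takes baseline data through March 2020, but no section dates a stop in follow-up visits. The Cognitive Correlates of Rumination section prints March 2021 for the recruitment stop.
- Visit 2 outstanding at the pause: baseline from about 16 December 2019 to 16 March 2020.
- Only Visit 3 outstanding: baseline from about 16 September to 15 December 2019.

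**Formula.** Earliest held visit = phone start + 6 months = 16 January 2021. Elapsed months = (earliest held visit − baseline) in days / 30.4375.

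**Visit 2 outstanding (label: 3 months)**
- Baseline 16 March 2020: 306 / 30.4375 = 10.1 months.
- Baseline 16 December 2019: 397 / 30.4375 = 13.0 months.
- Visit 3 follows three months later, at about 13 to 16 months.

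**Only Visit 3 outstanding (label: 6 months)**
- Baseline 15 December 2019: 398 / 30.4375 = 13.1 months.
- Baseline 16 September 2019: 488 / 30.4375 = 16.0 months.
- With Visit 2 on time, the Visit 2 to Visit 3 gap is 13.1 − 3 = 10.1 to 16.0 − 3 = 13.0 months, against a nominal 3.

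**Sensitivity to the start date**
- A 1 July start gives 291 / 30.4375 = 9.6 months at the short end for Visit 2. A 31 July start gives 412 / 30.4375 = 13.5 at the long end.
- A 1 October 2020 start gives 12.5 to 15.5 months.
- A participant outside the phone study who was seen on 13 July 2020 would have Visit 2 at only 3.9 to 6.9 months.

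**Who could be affected (illustration only).** Assume uniform accrual of 17 per month (the Northwestern plan, Protocol 4.5) to 34 per month (both sites equal).
- Visit 2 outstanding: 3 × 17 = 51 to 3 × 34 = 102, or 7% to 14% of 728.
- Visit 2 or 3 outstanding: 6 × 17 = 102 to 6 × 34 = 204, or 14% to 28% of 728.

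These are people with a visit due at the assumed pause. They are not counts of late visits that took place, and the mediation uses English-language participants only.

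**The printed Meaning and Purpose cut-off.** That analysis excludes enrolment on or after 16 September 2020. Adding 6 months gives 16 March 2021, which does not secure three assessments before the pandemic, the section's stated aim. A cut-off of 16 September 2019 would give 16 March 2020.

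**The case against.** The strongest reply is that the Protocol of July 2020 is a contingency plan, and nothing shows that a delayed in-person visit entered the data. Protocol 4.2 treats in-person assessments after the pandemic as only a possibility. The SAP says that the study collected additional longitudinal data on a subset of 304 instead of completing recruitment. Its 2024 section, written in the past tense, describes three-month spacing. The 10-to-13-month figure needs three conditions together: Visit 2 outstanding at the pause, joining a voluntary phone study, and returning afterwards. The October 2020 interim run cannot contain visits held to January 2021, so comparing the two runs is a partial check.

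Much of this stands. It limits the point to what the plan permits. It does not remove the gap, because the final run has no rule to keep late visits out or to show that there were none. The three-month spacing in the PCL-5 section may simply be the nominal schedule.

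Four stronger readings are tempting but unsupported:
- **That the factor analysis and PCL-5 Aim 2 are biased in the same way.** The factor analysis compares loadings by literacy and visit and estimates no lagged path. A spurious literacy difference would need delay to differ by literacy, and nothing shows that. Because mode is randomised, calendar effects should be broadly balanced between paper and touchscreen. PCL-5 Aim 2 relates demographics and baseline health literacy to later symptoms without naming the outcome visit, so it has no defined lag to distort.
- **That the Meaning and Purpose analysis is already protected.** As printed, its cut-off keeps people enrolled from December 2019 to March 2020 whose Visit 3 was late.
- **That the documents date the in-person stop at March 2020.** They do not, and they also print March 2021.
- **That restricting the set costs little.** The number of late visits is unknown.

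**Conclusion.** The point holds for the final sleep mediation. Followed as written, the plan can pool lags of about 3 months with lags of 10 months or more, and pre-pandemic with pandemic measurements, under one pair of labels. The visit labelled 3-month could fall at about 10 to 13 months, and the visit labelled 6-month at about 13 to 16 months. These are earliest dates, conditional on a mid-March 2020 pause, a July 2020 phone start, phone participation and a later return. If March 2021 is the correct stop, the ranges must be recalculated. The size and direction of any bias cannot be given, because neither the number of delayed visits nor their dates are stated. For the factor analysis and PCL-5 Aim 2 the matter warrants a sensitivity check and no more.

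**What to change.** 1. **Sleep mediation.** Report actual days since baseline for each visit. Run the analysis on visits within a stated window of the nominal date (or completed before the pause) alongside the all-visits analysis. Base any conclusion about a 3-month or 6-month lag on the in-window set.
2. **Three-visit factor analysis and PCL-5 Aim 2.** Add the same restriction as a sensitivity analysis only. If delayed visits are included, correct the PCL-5 section's description of three-month spacing.
3. **Dates.** Reconcile the 16 September 2020 cut-off with its stated aim of three assessments before the pandemic. Reconcile March 2020 (Meaning and Purpose DIF section) with March 2021 (Cognitive Correlates of Rumination section).

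The cost is SAP wording, the use of visit dates and one additional run per analysis. The restricted set loses participants, by a number that the documents do not allow one to estimate. If few visits were late, the two runs will agree and little is lost.

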- 4.14Cognitive impaired adults. Participants with severe cognitive impairment will be considered ineligible for this study. The research coordinator will administer a cognition screener (i.e., SPMSQ) that assess for any severe cognitive impairment to determine eligibility for this study. Participants with known mild-to-moderate cognitive impairment may be referred by clinicians to enhance our participant sample for the dementia supplement. Only those deemed capable of providing consent (based on the SPMSQ score) will be considered for the study and their diagnosis of mild-to-moderate cognitive impairment will be noted in the study's REDCap project.

5.0 Multiple sites:

- 5.1 Study sites. This study is being conducted at two sites: Northwestern University and Boston University Medical Center (BUMC). [name] is the PI of the Northwestern site and [name] is the PI of the BUMC site. Northwestern is the grant-holding site with [name] as the contact PI, but both PIs share overall leadership of the study. Both sites will recruit an equal number of participants (N = 608).
- 5.2 Required approvals. Recruitment will proceed at each individual site only when approved by the local IRB.
- 5.3 Site coordination. The sites are in frequency phone and email contact, and there is a weekly teleconference in place for the PIs and research coordinator to aid in consistency of study procedures. An all-team meeting is scheduled for once per month. To ensure that both sites are using the appropriate documents for the study, there is a shared, secure site on Box.com for all study materials (Note: No patient data or PHI is stored on Box, only study materials). Modifications to study protocols will be discussed among the team during the weekly teleconferences. These teleconferences will also be used to discuss problems, interim results, and eventual closure of the study.
- 5.4 Data management and security. The entire study team has been briefed on proper data management and security procedures. This includes the maintenance of data only on secure study trackers, managed via REDCap. Data security will be a weekly agenda item and data security will be routinely audited in terms of physical records (i.e., paper questionnaires and consent forms) as well as study files. Any and all non-compliance with the study protocol or applicable requirements will be reported to the appropriate IRBs in accordance with local policy.

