6.0 Incomplete Disclosure or Deception:

There is no deception or incomplete disclosure as part of this study.

Recruitment:

We plan to recruit no more than 608 participants. They will be recruited through Northwestern Medicine with the assistance of our physician coinvestigator, [name], and Northwestern Medicine Enterprise Data Warehouse (EDW). EDW contains clinical data from NMHC which is mined by a team of data analysts at Feinberg School of Medicine. The study team will work with the data analysts to define a cohort of patients to be recruited. Patients will then be contacted in accordance with NMHC and NU IRB policy including obtaining physician consent and sending an IRB and NMHC approved mailing (e.g., letter or email) before contacting patients either by phone or by email. The study team will screen for eligible participants using Epic, which is the electronic medical record that these clinics use. Via Epic, the research coordinator(s) will identify potential participants within our physician coinvestigator's schedule and request permission to approach their patients to assess eligibility and interest in the study. Participants will also be screened in clinic waiting rooms. Specifically, with approval from physicians and medical staff, research coordinators will approach potential research participants in Northwesternaffiliated clinics (e.g., Erie Family Health Center) and provide them with information about the study. The physician coinvestigators will also alert the coordinators of eligible participants. Interested participants will be invited to provide informed consent, and will then complete all the research measures relevant to the first visit in a private clinic room. Subsequently, they will be scheduled for their second and third visits. If needed, the research team will contact other physicians within General Internal Medicine at Northwestern Medicine for approval to contact their patients.

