Recruitment for the phone-based protocol will be from enrolled participants in the original protocol. We will recruit the entire cohort of 612 participants from the original protocol.

Participants will receive \$40 upon completion of the baseline visit, \$50 after the 3-month visit, and \$60 after the 6-month visit in the form of cash. In addition, they will receive parking passes at each one of their visits to cover the cost of their parking if they parked in a specified Northwestern garage. If needed, taxi or similar transportation (e.g., Lyft) will be arranged for participants, which will be paid for by the research project. Participants will receive up to \$22.50 for transportation costs. Additionally, participants will receive \$25 upon completion of the cognitive screening questions.

After Visit 1, the participant will receive the 1-page Summary Sheet of the research study as a retention material to remind participants of the importance of the research and what to expect next in the study. Additionally, after each visit the participant will receive a "Thank You Card" as a retention material. These "Thank You Cards" will be handwritten by the principal investigator to include the following text, "Thank you for your participation in our study. With your help, we will be able to talk to patients more clearly. We hope this work will help us provide better health care in the future. We couldn't do it without you!"

For the phone-based protocol, participants will receive \$40 upon completion of the baseline visit, \$50 upon completion of the 3-month follow-up, and \$60 upon completion of the 6-month follow-up. Payment will be made in the form of gift cards (either physical gift card mailed to the participant or e-gift card emailed to the participant, depending on participant preference).

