Using a large sample, we will determine the psychometric properties of health questionnaires across levels of health literacy. Testing will be conducted in English and Spanish, across two modes of administration (paper-and-pencil vs. talking touchscreen). Each participant will have three visits (baseline, 3-month, and 6-month follow-up), described below, in order to determine changes in psychometric properties over time. We will use *differential item functioning* (DIF) and other psychometric analyses to identify questionnaire items with varying characteristics across levels of health literacy. Before the COVID-19 pandemic, our original plan was to recruit $N = 1216$ participants for in-person assessments. At the time of this plan our final N is 728 participants who have completed a health literacy assessment; some of these participants are missing data on subsequent questionnaires. In-person recruitment was put on hold during the COVID-19 pandemic; in order to adapt the the pandemic, a subset of participants ($N = 304$) was invited to a phone-based protocol that included data collection about the impact of COVID-19, vaccine confidence, and health-related quality-of-life (PROMIS-29 profile).

- **Develop alternative modes of test administration that can better accommodate people with low health literacy.** National statistics indicate that 14% of adults in the United States have below basic reading skills, and over 75 million Americans have below basic or basic health literacy skills.¹⁴ These data strongly indicate that many individuals seeking health care will have difficulties with written questionnaires, even those that have been carefully developed such as those in the NIH PROMIS. We will test an alternative mode of administration that has been specifically designed to aid people of low health literacy – a computer-assisted “talking” version that uses speech technology that participants can privately access as needed to have items and response options

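### The protocol sets the Northwestern target and the phone-study size at 612, but its own recruitment cap and the two-site design give 608, and the SAP gives a phone sample of 304 or 300 without withdrawing the 612

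*Protocol*

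**What the plan says.** **In-person target.** Protocol section 4.5 reads "We aim to recruit 17 participants per month for three years to reach our local (i.e., Northwestern) target" and gives that target as 612. Section 5.1 reads "Both sites will recruit an equal number of participants (N = 608"), and the Recruitment section states "We plan to recruit no more than 608 participants". The SAP, under Study Objectives, says "our original plan was to recruit $N = 1216$ participants for in-person assessments", and its Table 2 lays out that design by site.

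**Phone study.** Section 4.5 says "We aim to enroll all 612 participants from the in-person protocol for the phone-based protocol". The Recruitment section agrees: "We will recruit the entire cohort of 612 participants from the original protocol". Section 3.0 makes enrolment in the in-person protocol, with all of its eligibility criteria, a condition of phone entry. It adds reliable phone access, willingness to take part in three phone sessions, adequate hearing and ability to complete consent.

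**What the SAP reports later.** In-person recruitment was put on hold during the pandemic. "At the time of this plan our final N is 728 participants who have completed a health literacy assessment", and "a subset of participants ($N = 304$) was invited to a phone-based protocol". The Study Design section of the SAP describes the same 304 as people on whom additional longitudinal data were collected. The vaccine-confidence addendum, the only phone-based analysis that the SAP specifies, uses 300.

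**The concern.** One protocol gives two figures for the same Northwestern target, and one of them is worded as a ceiling. The larger figure is then used as the size of a second study whose members must all come from the first. A team recruiting to the target in section 4.5 would exceed the limit in the Recruitment section, and section 5.4 commits the sites to reporting any non-compliance with the protocol to the IRBs.

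A reader who sets the protocol beside the SAP also finds two phone-study sizes that differ by about a factor of two. Nothing in the SAP says that the 612 has been superseded. The stake is a correct and consistent statement of sample size. No inferential result depends on it.

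**Working it through.** **1. Reproduce the protocol's figure.** Section 4.5 gives 17 per month for three years: 17 × 36 = 612. The multiplication is right.

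**2. Reproduce the design figure.** In SAP Table 2 each site has 8 groups of 76: 8 × 76 = 608. Two sites give 2 × 608 = 1216, the total in the SAP's Study Objectives. Section 5.1 taken alone could be read as 608 in total or 608 per site; Table 2 and the 1216 settle it as per site. So 608 is the design number.

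**3. Where 612 may come from.** 608 / 36 = 16.9 per month, which rounds to 17, and 17 × 36 returns 612. The protocol does not say so, but 612 looks like the product of a rounded monthly rate carried forward as a target.

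**4. Size of the conflict with the cap.** 612 − 608 = 4 participants, and 4 / 608 = 0.66%. The effect on any standard error is √(612/608) = 1.003, which is nil for practical purposes.

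**5. Consequence for the phone study.** Phone participants are a subset of in-person participants (section 3.0). If in-person enrolment is at most 608, phone enrolment is at most 608. The figure of 612 is therefore out of reach on the protocol's text alone, without using any later result.

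**6. What 612 would have required in practice.** It needed complete Northwestern accrual, plus consent, phone access and adequate hearing in every participant. The final two-site number with a health literacy assessment was 728. For Northwestern to supply 612 of these it would have had to contribute 612 / 728 = 84%, against a planned equal split. The actual site split is not given.

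**7. The phone sizes side by side.**

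| Source | Phone-study size | What it counts |
|---|---|---|
| Protocol 4.5 | 612 | aim to enrol, all in-person participants |
| Protocol, Recruitment | 612 | entire cohort |
| SAP, Study Objectives | 304 | subset invited |
| SAP, Study Design | 304 | subset with additional data collected |
| SAP, vaccine-confidence addendum | 300 | included in the analysis |

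The two SAP descriptions of 304 agree only if everyone invited provided data. The figure also occurs in the SAP as the planned size of each language group at a site (Table 2) and as the within-stratum number for the primary DIF analyses, so it needs a clear label.

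**The case against.** The strongest reply is that 612 against 608 is a four-person rounding difference, that 612 is only an aim, and that the SAP openly reports the recruitment hold, the failure to reach 1216, the 728 and the 304. A July 2020 aim set beside a later, explained outcome is not in itself a contradiction. Phone recruitment was only due to begin in July 2020, so the pool could have grown afterwards. Enrolment at the planned rate by the version date would have been about 17 × 28.4 = 483, but that count describes the start of phone recruitment and not its whole course. All of this stands, and it limits the weight of the point. It does not remove the conflict between 612 and a stated maximum of 608 in the same document, or the lack of any statement that the 612 was replaced.

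A reader might infer two stronger things.

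- **That phone-based intervals are about 1.4 times as wide as the protocol implies.** √(612/304) = 1.42 is correct, but it only compares two sample sizes. Neither document states a precision, power or effect-size target for the phone study, so no width is implied. The 612 is a Northwestern figure, and the documents do not say whether the 304 covers one site or both, so the two may not be like for like.
- **That the vaccine-confidence analysis was sized on 612.** It was not. The phone battery in the July 2020 protocol does not contain the Vaccine Confidence Index. That analysis was added to the SAP in March 2021 with its own sample of 300.

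**Conclusion.** The point holds as an inconsistency in stated sample size, and it is minor. The protocol gives 612 and 608 for the same Northwestern target. Because 608 is a cap and phone entry depends on in-person enrolment, the stated phone size of 612 cannot be delivered under the protocol's own text. The cap alone rules out 4 people (0.66%). The larger practical obstacle was the need for full accrual and 100% uptake during a recruitment hold, in a study that ended at 728 across two sites. The later 304 does not prove that 612 was impossible when written, and the conclusion does not rely on it.

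This rests on reading the Recruitment cap as applying to Northwestern, which is the setting that section describes and which agrees with Table 2. No specified analysis and no stated precision changes.

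**What to change.** 1. In protocol section 4.5, replace the target of 612 by 608. The recruitment rate may stay as about 17 per month if it is marked as rounded from 16.9.
2. In section 4.5 and the Recruitment section, replace the two phone-study statements of 612 by wording to the effect that all eligible enrolled in-person participants who consent will be included.
3. Restate the phone-study size to agree with the SAP's 304 and 300, and note in the SAP that these replace the protocol's 612. Say whether 304 is the number invited or the number with data, how 300 follows from it, and which sites it covers.

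The cost is wording only, in both documents. No participants, data or analyses are added. The stated phone size becomes smaller, which is the less favourable but accurate figure.
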